8. RESEARCH QUESTION AND OBJECTIVES

8.1. Objectives

8.1.1. Primary Objective

To examine the effect of at least 1 dose of Trumenba on gonococcal infection in adolescents and young adults of 15-30 years in the US.

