9. RESEARCH METHODS

9.1. Study Design

This is a retrospective cohort study using health care administrative claims data as described in Section 9.4 Data Sources.

Adolescents and young adults approximately 15 to 30 years of age at their individual time zero (calculated based on birth year) will be identified from administrative claims during 01 January 2016 and 31 December 2021.

The exposure cohort will be the individuals who have received at least 1 dose of Trumenba and at least 1 dose of MenACWY (Menactra[®], Menveo[®], or MenQuadfi[®]) prior to the Trumenba vaccination, between 01 January 2016 and 31 December 2021. The index date (zero time) for the exposed cohort is the last date of vaccination, and the cohort will be followed from 14 days after vaccination to the end of the study period (31 December 2022). The individuals in the cohort will be censored by the event of interest, death date (if known), plan disenrollment (if known) or the end of the study period, whichever comes first.

PFIZER CONFIDENTIAL CT24-WI-GL02-RF02 4.0 Non-Interventional Study Protocol Template For Secondary Data Collection Study 01-Jun-2022 Page 11 of 22

The reference cohort will be those with at least 1 dose of MenACWY vaccine, but no doses of Trumemba during the observation period, received between 01January 2016 and 31 December 2021. The MenACWY-only vaccinated cohort is used as a reference cohort rather than an unvaccinated cohort in order to help control for theoretical differences in health seeking and risk behaviors between vaccinated and unvaccinated individuals. The index date (zero time) of the reference cohort is the last dose of MenACWY and these individuals will be followed from 14 days after zero time until the earliest occurrence of the following: outcome of interest, death date (if known), plan disenrollment (if known) or 31 December 2022 (end of study period).

The outcomes of interest are gonococcal and chlamydial infections and only the first episode within the study period will be considered as event in case of repeated infections.

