9.7. Data Analysis

The zero time is the date of Trumenba vaccination for the exposed group and the date of MenACWY for the unexposed group. We will assess gonococcal infections that occurred between i) 14 days after zero time and 365 days ii) 14 days after zero time and 730 days, iii) 14 days after zero time and 1095 days, and iv) 14 days after zero time and till end of the study period (31Dec2022). We will censor the data in the event of interest, death date (if known), plan disenrollment (if known), target end date, or the end of the study period, whichever comes first. In descriptive analyses, we will fit Kaplan-Meier curves. We will also create unadjusted and covariate adjusted Cox proportional hazard regression models verifying first that the proportionality assumption was satisfied for all independent variables. Hazard ratios (HRs) will be estimated by exponentiation of the coefficient for the vaccine variable in these models, with vaccine effectiveness estimated as (1–HR)×100%. SEs for the coefficients will be used to estimate p values and CIs for the HRs. If a covariate does not satisfy the assumption of proportionality, we will exclude the variable for the multivariable model and will perform the stratified analysis using the covariate.

Detailed methodology for summary and statistical analyses of data collected in this study will be documented in a statistical analysis plan (SAP), which will be dated, filed and maintained by Pfizer. The SAP may modify the plans outlined in the protocol; any major modifications of primary endpoint definitions or their analyses would be reflected in a protocol amendment.

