2.1 STUDY DESIGN

This is a retrospective cohort study including individuals 15 to 30 years of age enrolled in a health plan covered by IQVIA PharMetrics® Plus during 1 Jan 2016 to until the latest release of the data (October 2022). The study is to estimate the effect of Trumenba vaccination on the disease of interest, in particular, the gonococcal incidences will be compared between the recipients of Trumenba + MenACWY vaccines and the recipients of MenACWY vaccine.

The exposure cohort will be the individuals who have received at least one dose of Trumenba and at least one dose of MenACWY between 1 January 2016 and 31 December 2021. The non–exposure or reference cohort will be the individuals with no dose of Trumenba but at least one dose of MenACWY vaccine received during the same time period.

PFIZER CONFIDENTIAL CT24-WI-GL03-RF03 2.0 Non-Interventional Statistical Analysis Plan For Secondary Data Collection Study 01-Jun-2020 Page 4 of 28 The date of index vaccination (zero time) for the exposed cohort is the date of the last dose of Trumenba vaccination, after at least one dose of MenACWY. Trumemba and MenAWCY will be identified by Current Procedural Terminology® (CPT) codes and National Drug Codes (NDC) listed in Appendix Tables 4 and 3, respectively. The index date of the unexposed cohort is the first date of MenACWY vaccination. The diseases of interest are gonococcal infection and chlamydia infections occurring at least 14 days after the zero time. International Classification of Diseases, Tenth Revision, Clinical Modification (ICD-10-CM) codes listed in Appendix Table 1 and 2 will identify gonococcal and chlamydia infections, respectively. Only the first episode will be considered as the event in case of repeated infections. Individuals will be followed until the earliest occurrence of the following: outcome, at death date (if known), at plan disenrollment or end of study period.

Study population

This is a retrospective cohort study and the study population are adolescents and young adults approximately 15 to 30 years of age at their date of vaccination (calculated based on birth year) and will be identified from administrative claims during 01 January 2016 and 31 December 2021.

Data source

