5.3.2 Exploratory Endpoints

 VE calculated as 1 minus the hazard ratio for gonococcal infection between the recipients (aged 16-23 years) of both Trumenba (at least one dose) and MenACWY (at least one dose) vaccines and the recipients (aged 16-23 years) of MenACWY vaccine only multiplied by 100, adjusted for potentially confounding variables (age, sex, and US region, as appropriate).

In this analysis, the cases are those who had at least one claim of gonococcal infection in the database. Each individual will be followed until the end of the follow-up period, censoring the follow-up at death date (if known) or plan disenrollment (if known).

PFIZER CONFIDENTIAL

CT24-WI-GL03-RF03 2.0 Non-Interventional Statistical Analysis Plan For Secondary Data Collection Study 01-Jun-2020 Page 10 of 28 2. VE calculated as 1 minus the hazard ratio for gonococcal infection between the recipients (aged 15-30 years) of both Trumenba (at least one dose) and MenACWY (at least one dose) vaccines and the recipients (aged 15-30 years) of MenACWY vaccine only multiplied by 100, adjusted for potentially confounding variables (age,sex, and US region).

In this analysis, the cases are those who had at least one claim of gonococcal infection in the database. Each individual will be followed for the outcome from 14 days after their zero time until the end of the follow-up period, censoring the follow-up at death date (if known) or plan disenrollment (if known).

The analysis will be carried out by different periods of study (zero time to 12 months post zero time, zero time to 24 months post zero time, zero time to 36 months post zero time, and zero time to 48 months post zero time)

Variable	Role	Operational definition
Age (years)	Baseline characteristic and potential confounder	Age will be calculated based on the 1 st date of Trumenba vaccination for the exposed cohort and the date of the 1 st dose of MenACWY for the unexposed cohort
Sex	Baseline characteristic and potential confounder	Sex will be categorized as female and male
US region	Baseline characteristic and potential confounder	US region which is categorized as : E=Northeast S=South MW=Midwest W=West

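### Exposed follow-up starts at the last Trumenba dose in every analysis, so the primary ≥1-dose VE measures time after the final recorded dose

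*SAP*

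**What the plan says.** The primary objective (Protocol 8.1.1, repeated in SAP 2.2.1) is "To examine the effect of at least 1 dose of Trumenba on gonococcal infection". SAP 7.2.1.1 classes a person as exposed with one or more Trumenba doses plus one or more MenACWY doses. It counts infections from 14 days after zero time to the end of the study.

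Zero time for the exposed cohort is described in three ways:

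- SAP 2.1: "The date of index vaccination (zero time) for the exposed cohort is the date of the last dose of Trumenba vaccination", given after at least one MenACWY dose.
- Protocol 9.1: "The index date (zero time) for the exposed cohort is the last date of vaccination".
- Protocol 9.7: "The zero time is the date of Trumenba vaccination for the exposed group", with no dose number.

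The SAP covariate table (5.4) uses a different date for age: "Age will be calculated based on the 1 st date of Trumenba vaccination for the exposed cohort".

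The ≥2-dose analysis (SAP 7.4.2.1.1) refers back to 7.2.1.1 and has no zero time of its own. For the reference cohort, SAP 2.1 says "The index date of the unexposed cohort is the first date of MenACWY vaccination", while Protocol 9.1 uses the last MenACWY dose.

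**The concern.** A person meets the ≥1-dose definition at the first eligible Trumenba dose. If follow-up starts at the last dose, a person with several doses has a stretch of time that fits the primary exposure definition but is not analysed. It cannot move to the reference cohort, because that cohort excludes Trumenba recipients.

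Take two people who each receive dose 1 in January and have gonorrhoea in April. One receives dose 2 in July and the other never returns. The infection is a primary event for the second person and is before zero time for the first. Exposure at the time of infection was the same, so inclusion of the event turns on something that happened later.

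At stake is the meaning of the primary estimate. It would be reported as the effect of at least one dose, but one-dose experience would come only from people with no further recorded dose. Exploratory endpoint 2 has the same problem: its 12-month window would run from the final dose, not from the start of exposure.

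**Working it through.** **Does anything in the plan restore the omitted time?** SAP 7.2.1.1 mentions a time-varying approach and a model using entry and exit dates. It does not define the approach, and nothing says that time between doses re-enters. The only primary sensitivity analysis (SAP 7.2.1.2) removes co-infections. No analysis starts at the first dose.

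**The plan's own figure.** SAP 3 gives 500,000 people, 15% exposed, risks of 0.0036 and 0.0048, HR 0.80, two-sided alpha 0.05 and power of 94%.

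- Events: 75,000 × 0.0036 = 270 exposed; 425,000 × 0.0048 = 2,040 reference; m = 2,310.
- Allocation ratio k = 75,000/425,000 = 0.1765.
- Freedman-type formula, taken to be the one behind the named package: power = Φ(√(k·m)·|HR − 1|/(k·HR + 1) − 1.960) = Φ(20.19 × 0.20/1.1412 − 1.960) = Φ(1.58) = 94.3%. The stated figure is reproduced.

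**Inputs the documents do not give.** These are assumed: f, the share of exposed people with two or more doses; g, the mean gap from first to last dose; F, mean follow-up after the last dose; and VE after one dose and after two. With a 14-day lag under either start date, the time lost per multi-dose person is g.

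*Set A: f 0.4–0.8, g 0.5–1 year, F 1.5–2.5 years.*

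- Discarded share s = f·g/(f·g + F): from 0.2/2.7 = 7% to 0.8/2.3 = 35%.
- Suppose VE is 10% after one dose and 30% after two, with a constant baseline hazard. VE from the last dose is 10 + 20f. Adding back the one-dose time lowers it by s × 20f.
- Low end: 0.074 × 0.4 × 20 = 0.6 points (18.0% against 17.4%).
- Middle (0.6, 0.75, 2): s = 0.45/2.45 = 0.184, so 0.184 × 0.6 × 20 = 2.2 points.
- High end: 0.348 × 0.8 × 20 = 5.6 points (26.0% against 20.4%).

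*Set B: f 0.3–0.7, gap 1–12 months, follow-up T from the first dose 1.5–3 years.*

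- Discarded share f·g/T: from 0.3 × (1/12)/3 = 0.8% to 0.7 × 1/1.5 = 47%; 12.5% at f = 0.5, 6 months and 2 years.
- With the same 20-point gradient, T = 2 years and gaps of 2–12 months, the last-dose VE is 0.1 to 3.8 points higher. In the middle case it is 18.6% against 17.5%, or 1.1 points.

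**No gradient.** With VE of 20% after every dose and a constant hazard, both start dates give 20% and the shift is zero.

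**Power.** If the 270 events are counted from the last dose, a first-dose start under set B gives 272 to 506 exposed events (middle case 270/0.875 = 309). Power is then 94.3% to 96.0%, a change of under 2 points.

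**The case against.** The best case against acting is that the study is declared exploratory, with no hypothesis tested, and that every input to the size is assumed. This stands as a limit on magnitude. The background section gives no dose gradient for the fHbp vaccine, only a single estimate of 3%. The gradient it does give, for 4CMenB, is 26% to 40%, or 14 points. Using 14 in place of 20 in set A gives 0.074 × 0.4 × 14 = 0.4 to 0.348 × 0.8 × 14 = 3.9 points. None of this removes the mismatch between the stated question and the follow-up analysed.

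Four stronger readings are tempting and are not supported:

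- *Immortal-time bias.* The interval between doses is left out. It is not credited to the exposed cohort as event-free time.
- *VE is overstated.* This holds only if protection rises with doses. If protection wanes after dose 1, dropping the early time could lower VE.
- *The index could be a later MenACWY dose.* The wording in Protocol 9.1 is loose, but read with Protocol 9.7 and SAP 2.1 it means Trumenba.
- *A known number of events is lost.* SAP 3 does not say from which dose the 0.0036 risk runs. If it runs from the last dose, set A implies 270 × 0.2/2.5 = 22 to 270 × 0.8/1.5 = 144 further events under a first-dose start. If it runs from the first dose, the 270 would shrink instead.

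It is also fair that people with two or more doses belong to both analyses whatever the start date, and that their time after dose 2 would stay in both. Overlap between the primary and first secondary analyses is not itself the fault.

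**Conclusion.** The point holds on the text alone. As written, the primary analysis estimates VE after the final recorded dose among people with at least one dose, and which infections count depends on later doses. This is a fault in what is estimated, not in precision.

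Its size cannot be determined from the documents. About 0 to 6 VE points is illustrative, against a design target of 20%. The upper end needs 80% of exposed people with two or more doses, a one-year mean gap, only 1.5 years of later follow-up and a 20-point gradient all at once; the middle cases give 1 to 2 points. People with a single dose are unaffected.

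A reader cannot assume that last-dose indexing was settled deliberately for all analyses, since Protocol 9.7 names no dose and SAP 5.4 takes age at the first. These passages need reconciling in any event.

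**What to change.** In Protocol 9.1 and 9.7 and SAP 2.1, tie zero time to the dose that confers the exposure:

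- ≥1-dose analyses: the first eligible Trumenba dose, that is, after MenACWY.
- ≥2-dose analyses: the second Trumenba dose.
- Follow from 14 days later, and do not let later doses reset follow-up.
- Calculate age at the same zero time.

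In the same edit, reconcile the reference index date (last MenACWY dose in Protocol 9.1, first in SAP 2.1). Changing the exposed date alone would leave the protocol comparing a first-dose start with a last-dose start. Also state what the time-varying approach in SAP 7.2.1.1 means. Keep the last-dose version as a sensitivity analysis.

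The cost is one more date derivation on existing data and wording changes in both documents. Protocol 9.7 and SAP 2 call for a protocol amendment if the change to the primary analysis counts as major. The primary estimate may be slightly less favourable if protection needs more than one dose; the ≥2-dose objective would show that separately.

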2.2 STUDY OBJECTIVES

2.2.1 Primary Objectives

• To examine the effect of at least one dose of Trumenba on gonococcal infection in adolescents and young adults of 15-30 years in the United States

2.2.2 Secondary Objectives

- To examine the effect of at least two doses of Trumenba on gonococcal infection in adolescents and young adults of 15-30 years in the United States
- To examine the effect of at least one dose of Trumenba on chlamydial infection in adolescents and young adults of 15-30 years in the United States
- To examine the effect of at least two doses of Trumenba on chlamydial infection in adolescents and young adults of 15-30 years in the United States

2.2.3 Exploratory Objectives

- To examine the effect of at least one dose of Trumenba on gonococcal infection in adolescents and young adults of 16-23 years in the United States
- To examine the effect of at least one dose of Trumenba on gonococcal infection in adolescents and young adults of 15-30 years in the United States at 12 months, 24 months, 36 months and 48 months following the index vaccination

3 HYPOTHESES AND DECISION RULES

PFIZER CONFIDENTIAL CT24-WI-GL03-RF03 2.0 Non-Interventional Statistical Analysis Plan For Secondary Data Collection Study 01-Jun-2020 Page 6 of 28 This is an exploratory study, thus no hypothesis will be tested. There will be more than 500,000 individuals in which approximately 15% will be the experimental group. Assming a total of 500,000 subjects, and the probability of failure in the experimental group over the maximum time period of the study is 0.0036 and the probability of failure in the control group over the maximum time period of the study is 0.0048. This provides a power of 94% assuming a hazard ratio of 80% (20% vaccine effectiveness) and at an alpha of 0.05. The calculation was made using "powerSurvEPI" package under RStudio (Version 1.1.453).

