9.5. Study Size

This is an exploratory study, thus no hypothesis was generated. All eligible individuals will be included in the study.

For the sample size estimation, we wished to detect a vaccine effectiveness against gonococcal infection of 20% or more with an onset from 14 days after receipt of both TRUMENBA and MenACWY. A Cox regression of the log hazard ratio on a covariate with a standard deviation of 1.50 to achieve 80% power at a 0.05 significance level to detect a regression coefficient equal to -0.2200, we need a sample of 15,669. The sample size was adjusted for an anticipated overall event rate of 0.0046. We will have 520,392 samples in the study database illustrating that we have adequate samples to conduct the analysis.

PFIZER CONFIDENTIAL

CT24-WI-GL02-RF02 4.0 Non-Interventional Study Protocol Template For Secondary Data Collection Study 01-Jun-2022 Page 17 of 22

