3.2 STATISTICAL DECISION RULES

The alpha level will be 0.05, 2-sided. No adjustments for multiple comparisons will be made.

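### The SAP's 94% power pairs failure probabilities that imply a hazard ratio of 0.75 with a target of 0.80, and applies what it calls maximum-period risks to everyone

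*SAP*

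**What the plan says.** SAP section 3 takes 500,000 people, of whom "approximately 15% will be the experimental group". It assumes that "the probability of failure in the experimental group over the maximum time period of the study is 0.0036" and that "the probability of failure in the control group over the maximum time period of the study is 0.0048". It then concludes: "This provides a power of 94% assuming a hazard ratio of 80% (20% vaccine effectiveness) and at an alpha of 0.05". Section 3.2 makes the alpha two-sided. The software is given as the R package powerSurvEPI, without naming the function. The SAP gives no expected number of events, no distribution of follow-up and no disenrolment rate.

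On follow-up, SAP section 2.1 and protocol section 9.1 put the qualifying vaccinations between January 2016 and December 2021 and censor people at plan disenrolment. The protocol ends follow-up on 31 December 2022; the SAP refers to a data release of October 2022. Protocol section 9.5 separately uses "an anticipated overall event rate of 0.0046" and also names a vaccine effectiveness of 20% as the effect to detect.

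**The concern.** Two features of the SAP paragraph do not fit together.

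- **Effect size.** Both probabilities are defined over one common period. Under proportional hazards two such risks fix the hazard ratio, and here they fix it at 0.75 (effectiveness 25%), not the stated 0.80 (effectiveness 20%).
- **Period.** The probabilities are described as risks over the longest possible follow-up, yet the stated power is reproduced only if they are multiplied by the whole cohort. Someone indexed in early 2016 who stays enrolled has about 7 years; someone indexed in December 2021 has at most about 1 year.

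The 94% is the SAP's only planning figure. If estimated effectiveness is near zero, readers will use it to judge whether a 20% effect could have been missed. They need to know whether it rests on about 2,300 events or on far fewer.

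**Working it through.** **Inputs (SAP section 3 unless noted).** N = 500,000; 15% exposed, so 75,000 exposed and 425,000 reference, k = 75,000/425,000 = 0.1765; risks 0.0036 and 0.0048; HR 0.80; two-sided alpha 0.05 (SAP section 3.2).

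**1. Reproduce the 94%.** Events: 75,000 × 0.0036 + 425,000 × 0.0048 = 270 + 2,040 = 2,310. The Freedman-type formula for unequal groups is

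power = Φ( √(k·m) · |HR − 1| / (k·HR + 1) − 1.96 ).

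With m = 2,310 and HR = 0.80: √407.6 = 20.19; 20.19 × 0.20 / 1.1412 = 3.54; Φ(1.58) = 94.3%. Of the forms tried, only this one matches: Schoenfeld's formula gives 96.9%, a comparison of the two proportions 99.7%, and the one-sided Freedman form 97.1%. That this formula was used is therefore an inference from the match. It takes the two probabilities only to count events and takes the effect from the separately entered 0.80, so nothing in it forces the inputs to agree.

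**2. Hazard ratio implied by the risks.** ln(1 − 0.0036)/ln(1 − 0.0048) = 0.7495; the simple ratio is 0.0036/0.0048 = 0.75.

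**3. Power once the inputs agree (same formula).**

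| Inputs | Events | Power |
|---|---|---|
| HR 0.80, reference 0.0048, exposed 0.80 × 0.0048 = 0.00384 | 288 + 2,040 = 2,328 | 94.4% |
| HR 0.80, exposed 0.0036, reference 0.0036/0.80 = 0.0045 | 270 + 1,912.5 = 2,182.5 | 93.0% |
| HR 0.75, risks as stated | 2,310 | 99.4% |

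**4. If the risks are true maximum-period risks.** Assumptions, none of them in the documents: uniform entry over the 6 years, constant hazard, follow-up to 31 December 2022, HR 0.80 with exposed risk 0.00384.

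- *No disenrolment.* Follow-up runs from 1 to 7 years, mean 4.0. Events: 2,328 × 4/7 = 1,330. Power: √(0.1765 × 1,330) = 15.32; 15.32 × 0.20/1.1412 = 2.685; Φ(0.725) = 77%. Schoenfeld: √(1,330 × 0.15 × 0.85) × 0.2231 = 2.906; Φ(0.946) = 83%. Allowing for the 14-day lag gives 1,325 events and 76%; ending in October 2022 gives 76%.
- *Disenrolment at an assumed constant rate of 0.20 per year.* Mean follow-up is 2.6 years, about 870 events, power 58% (Schoenfeld 65%). Rates of 0.10 and 0.30 give 67% and 51% (Schoenfeld 74% and 57%).
- For reference, 80% power by the matching formula needs about 1,448 events, 62% of 2,328.

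**5. If the risks are crude proportions over actual follow-up.** The SAP mix is 0.15 × 0.0036 + 0.85 × 0.0048 = 0.00462, which agrees with the protocol's 0.0046. Then 0.0046 × 500,000 = 2,300 events and power of roughly 94% stands. A crude ratio of 0.75 is compatible with HR 0.80 if mean exposed follow-up is 0.75/0.80 = 0.9375 of reference follow-up, about 6% shorter.

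**The case against.** The strongest reply is that the paragraph reaches the right answer. The power is stated explicitly for 20% effectiveness, protocol section 9.5 names the same 20%, and aligning the inputs at 0.80 changes the result by about one percentage point at most. All of that stands. A reader might infer that the 94% is a miscalculation, or that 25% may have been the intended effect. The documents support neither: the figure reproduces, and 25% appears nowhere.

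A second reply is that the risks may be crude proportions over unequal follow-up, in which case 0.75 need not equal the hazard ratio. The SAP indexes exposed people at their last Trumenba dose and reference people at their first MenACWY dose, and protocol section 7 reports MenB coverage rising from 14% in 2017 to 32% in 2021. Exposed follow-up about 6% shorter is therefore conceivable, though not documented. The agreement of 0.00462 with 0.0046 supports this reading without proving it. It does not save the text, because it makes the maximum-period description false.

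Third, the study is exploratory, tests no hypothesis and takes every eligible person from an existing database, so no sample size or decision rule depends on the 94%. That limits the severity, but it does not make the description correct.

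**Conclusion.** The point holds, and its severity is minor. The SAP paragraph is wrong as written on either reading. If the probabilities are maximum-period risks, they conflict with HR 0.80 and overstate the events when applied to 500,000 people. If they are crude proportions, the stated period is wrong.

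The ratio mismatch by itself is nearly harmless: 93.0% to 94.4% at HR 0.80. The period is what could matter, and its size depends on a fact the documents do not give. On the maximum-period reading, power is about 77% (83% by Schoenfeld) before disenrolment and 58% (65%) at an assumed 20% per year. On the crude-proportion reading it stays at roughly 94%.

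A reader might infer from the lower figures that the study is underpowered. The documents do not support that. Those figures need the 7-year reading, uniform entry and, for the lowest, a disenrolment rate that neither document states, while the one available cross-check, the protocol's event rate, favours the crude-proportion reading. That event rate agrees with the SAP's inputs and is not itself an error.

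**What to change.** Keep HR 0.80 as the target effect, and state the source of the two probabilities and the follow-up they cover.

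- *If they are maximum-period risks:* replace 0.0036 with 0.00384, and restate power from the expected number of events, using mean follow-up and the disenrolment seen or assumed in the database.
- *If they are crude proportions over actual follow-up:* say so, remove the maximum-period wording, state the expected events (about 2,300), and give the follow-up difference between cohorts that reconciles a ratio of 0.75 with HR 0.80. If there is no such difference, use 0.00384.

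Name the function used. Keep the event rate in protocol section 9.5 consistent with the figures chosen: with 0.00384 the mix becomes 0.15 × 0.00384 + 0.85 × 0.0048 = 0.004656, which rounds to 0.0047 rather than 0.0046.

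The cost is a few figures and sentences, plus a look at follow-up time in data already held. The cohort, endpoints and models are unchanged.
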